13.2.2. Statistical analysis methods

Primary study outcome – change from baseline in clinic SBP value tot Visit 4 will be estimated with 95% confidence interval construction.

In addition, clinic SBP (DBP) change from baseline will be assessed and evaluated using Mixed model repeated measures (MMRM) methodology [30, 31]. The multiple visits for each patient will be incorporated as repeated measures within each patient. Visit will be treated as a categorical predictor and baseline SBP (DBP) will be included as a covariate. An appropriate covariance structure will be selected to provide estimates (Least Square Means) of change from Baseline and to perform statistical analysis at Visit 4. The dose-response trend hypothesis test will be conducted using the appropriate contrast statement for a linear (ordinal dose) trend. In addition, Least Squares Means, the associated standard errors and 95% confidence intervals will be displayed by each individual dose group.

Patients who reached target level of SBP (DBP) at visits 2, 3 and 4 will be presented using frequencies and percentages for the study population. Patients who respond to therapy at visits 2, 3 and 4 will also be presented using frequencies and percentages. Secondary and exploratory outcomes will be analysed using descriptive statistics and frequencies and percentages as follows:

- Changes in systolic BP (SBP) during the treatment with Edarbi® (V2-V3) will be calculated and presented in summary tables using descriptive statistics for continuous variables;
- Changes in diastolic BP (DBP) during the treatment with Edarbi® (V2, V3) will be calculated and presented in summary tables using descriptive statistics for continuous variables;
- Percentage of patients who achieve target SBP<140 mm Hg (V2, V3, V4) will be described and presented in summary tables using absolute frequencies and percentages as well as 95% confidence intervals,
- Percentage of patients who achieve target DBP<90 mm Hg (V2, V3, V4) will be described and presented in summary tables using absolute frequencies and percentages as well as 95% confidence intervals;
- Percentage of patients who respond to Edarbi® therapy (defined as decrease of SBP \geq 20 mm Hg or decrease of DBP \geq 10 mm Hg; V2, V3, V4) will be described and presented in summary tables using absolute frequencies and percentages as well as 95% confidence intervals;
- Percentage of patients who achieve target BP (defined as SBP<140 mm Hg, DBP<90 mm Hg; V2, V3, V4) will be described and presented in summary tables using absolute frequencies and percentages as well as 95% confidence intervals;

- **Company Confidential Information**

Company Confidential Information

[REDACTED]

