9.5 The study plan (plan of observation)

A physician makes the decision to prescribe Edarbi® to a patient. Afterwards the physician evaluates inclusion/exclusion criteria and offers the patient participation in the observational study.

The investigator gives the patient necessary information about the study and asks the patient to read the Patient Information Sheet and Informed Consent Form. If the patient agrees to participate in the study then the patient and the investigator sign the Inform Consent Form and the investigator includes the patient in the study.

During participation in the study patients are observed according to the local routine practice. The assignment of a particular therapeutic strategy to the patient including all diagnostic procedures is decided in accordance with Russian guidelines "Diagnostics and treatment of hypertension" (2010) and Kazakh protocol on clinical diagnosis and treatment of hypertension (2013) [6, 7] and local routine practice. The patients would take Edarbi® according to local SmPC.

[figure not shown]
Due to the non-interventional study design it's not possible to appoint exact times for the study visits, although it is expected that the period of observation will be approximately 6 months. The frequency of the visits will be assigned by each physician according to their routine practice. It is anticipated that the patients will visit their physician every 3 months and more often at the beginning until the patient achieves target blood pressure. Information for the study will be collected from 4 patients' visits to the physician:

- Visit 1 (Baseline visit): is carried out after the physician made the decision to prescribe medication and the patient signed the Informed Consent Form. Baseline visit is the visit when the patient was prescribed appropriate medication.
- Visit 2 (Observational visit): assessment of blood pressure dynamics, data collection is performed approximately one month after therapy beginning
- Visit 3 (Observational visit): assessment of blood pressure dynamics, data collection is performed approximately 3 months after therapy beginning
- Visit 4 (Final observational visit): assessment of therapy effectiveness. Data collection is performed approximately 6 months after therapy beginning

Last visit can occur later than 6 months after baseline but not more than 7 months total.

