10.6.1. Documentation of the study medication

Due to non-interventional design of the study, the decision about particular HTN treatment strategy to the patient is taken by attending physician. Treatment of interest is Edarbi®. The study medication is not provided by the sponsor.

Edarbi® treatments will be registered in the CRF. The following information about Edarbi® treatment will be collected:

- start date of Edarbi®,
- end date of Edarbi® treatment or prolongation of Edarbi® treatment,
- single and total dose, dose regimen,
- reason(s) for discontinuation of Edarbi® treatment (if applicable).

Edarbi® should be administered according to the official prescribing information (The Russian SmPC). The starting dosage will be 40 mg per day. In case of insufficient efficacy the dosage could be increased up to 80 mg per day.

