13.4 Determination of Sample Size

Sample size was calculated for the primary objective of the study: to estimate the effect of Edarbi® treatment on blood pressure for patients with increased weight or obesity. This estimation will be conducted with 95% confidence interval construction. Sample size was calculated using SAS 9.3 proc power procedure (Confidence Interval for Paired Mean Difference) for following parameters (fixed scenario elements):

Fixed Scenario Elements	
Distribution	Normal
Method	Exact
Alpha	0.05
CI Half-Width	1
Standard Deviation	17.79
Correlation	0.4375
Nominal Prob(Width)	0.9
Number of Sides	2

Prob Type	Conditio nal
------------------	-------------------------

Where the distribution is assumed to be normal, alpha specifies the level of significance, Nominal Prob (Width) specifies the desired probability of obtaining a confidence interval half-width less than or equal to the value specified as CI Half-Width. Half-width of the desired confidence interval was set to 1 mm Hg. Standard deviation and correlation coefficient were estimated by pooling recent studies data [12, 13, 14, 19, 20] for clinic Systolic Blood Pressure after at least 6 weeks of antihypertensive treatment with azilsartan medoxomil. Pooled effect estimation (clinic SBP difference at the end of the treatment from baseline SBP value) is -17.311 with pooled SD of 17.7887, which corresponds to the standardized difference of -0.9731 and correlation coefficient of 0.4375. For the denoted scenario, it is required to receive data from at least 1437 patients before-after the treatment.

Computed N Pairs	
Actual	N
Prob(Width)	Pairs
0.903	1437

Taking into account a possible dropout of 25%, it is recommended to enrol at least 1916 patients into the study.

According to the reference studies [24-29], the SD for effect for DBP is less than the SD for SBP, so the denoted number of patients will be sufficient for the corresponding secondary outcomes.

14 Reports

A Non-Interventional Study Report based on the results obtained will be prepared and submitted to the Sponsor for distribution. The Final Study Report should be available within one year from collection of the last data point, and the participating sites should be informed about the results when the report is finalised. Composed the study report should be provided to the IEC.

15 Publications

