9.1. Statistical Analysis of the Primary Efficacy Variable(s)

Primary study outcome – change from baseline in clinic SBP value to Visit 4 will be estimated with 95% confidence interval construction and analyzed with paired t-test in pairwise comparison with baseline SBP

Changes in systolic BP (SBP) during the treatment with Edarbi[®] will be evaluated from baseline to Month 1,3 and 6. Additionally the changes of SBP from baseline to mentioned visits will be analyzed with paired T-test in pairwise comparisons with baseline level of the variable.

In addition, clinic SBP (DBP) change from baseline will be assessed and evaluated using Mixed model repeated measures (MMRM) methodology. The multiple visits for each patient will be incorporated as repeated measures within each patient. Visit will be treated as a categorical predictor and baseline SBP (DBP) will be included as a covariate. An appropriate covariance structure will be selected to provide estimates (Least Square Means) of change from Baseline and to perform statistical analysis at Visit 4 (Month 6). In addition, Least Squares Means, the associated standard errors and 95% confidence intervals will be displayed by each individual dose group (in case if exposition assessment will reveal distinct dose groups, then group factor and group * visit interaction will be added to the model).

Patients who reached target level of SBP (DBP) at visits 2, 3 and 4 will be presented using frequencies and percentages for the study population.

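### The supportive MMRM forces one baseline slope on all three visits; if the true slopes differ and dropout depends on baseline BP, its Visit 4 LS mean is biased, by roughly 0.2 to 0.5 mm Hg under moderate assumptions

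*Protocol*

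**What the plan says.** The primary result is the observed change in clinic SBP to Visit 4, which "will be estimated with 95% confidence interval construction" (protocol 13.2.2). SAP 9.1 adds a paired t-test. The MMRM comes second: "In addition, clinic SBP (DBP) change from baseline will be assessed and evaluated using Mixed model repeated measures (MMRM) methodology". Its fixed effects are given in one sentence, identical in both documents: "Visit will be treated as a categorical predictor and baseline SBP (DBP) will be included as a covariate". SAP 9.1 does name an interaction where one is wanted. If distinct dose groups emerge, "then group factor and group * visit interaction will be added to the model". No such term is named for baseline.

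The covariance is left open: "An appropriate covariance structure will be selected to provide estimates (Least Square Means) of change from Baseline". Neither document says at which baseline value the LS means are to be evaluated.

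There are three post-baseline visits ("Information for the study will be collected from 4 patients' visits to the physician", the first being baseline). Protocol 13.4 gives one correlation between baseline and end of treatment (0.4375) and inflates the sample: "Taking into account a possible dropout of 25" per cent. SAP section 5 assumes that missing efficacy outcomes are MAR.

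**The concern.** With main effects only, the regression of change on baseline BP must be the same at Months 1, 3 and 6. The slope at a visit is r × SD(visit)/SD(baseline) − 1, which is r − 1 when the SDs are equal. If the correlation with baseline weakens over six months, the true slope steepens. The fitted common slope is then an average that is too shallow at Visit 4, the visit reported.

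With complete data this does no harm. With dropout related to baseline, the patients seen at Visit 4 no longer have the overall mean baseline, and the model uses the wrong slope to carry them back to it. Missingness that depends only on baseline, a variable already in the model, is the simplest MAR case, and this specification can fail it.

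Some features of the study make the conditions conceivable. Treatment may be intensified ("In case of insufficient efficacy the dosage could be increased up to 80 mg per day"). Stopping the drug ends data collection (protocol 9.4.5.1), and treatment failure is a listed reason for dropout (protocol 13.2.1). None of these establishes either condition.

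**Working it through.** **The plan's own figure.** Inputs from protocol 13.4: SD 17.79, correlation 0.4375, half-width 1 mm Hg, probability 0.9, alpha 0.05.

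- SD of the paired difference = 17.79 × √(2 × (1 − 0.4375)) = 18.87.
- The exact conditional method gives 1437 pairs with probability 0.903, as stated.
- 1437/0.75 = 1916, as stated.
- SE of the paired mean = 18.87/√1437 = 0.50 mm Hg.

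The documents give no figure for MMRM bias, so the rest needs assumptions.

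**Assumptions.** Equal SDs at all visits; Visit 4 correlation held at 0.4375, so the true Visit 4 slope is −0.5625; Visit 2/3 correlations varied; unstructured covariance; 25% monotone dropout depending on baseline SBP only, with an odds ratio (OR) per baseline SD; LS mean evaluated at the mean baseline of everyone enrolled. The models were fitted by maximum likelihood to large simulated samples, with SEs scaled to 1916 patients.

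**Approximate formula.** Bias ≈ (common slope − Visit 4 slope) × (overall mean baseline − mean baseline of patients seen at Visit 4).

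For Visit 2/3 correlations 0.65/0.55 and OR 2, the fitted common slope is −0.419 and patients seen at Visit 4 start 3.14 mm Hg below the overall mean. The product is (−0.419 + 0.5625) × 3.14 = 0.45 mm Hg. For 0.55/0.50 and OR 2 it is (−0.493 + 0.5625) × 3.12 = 0.22.

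**Simulated Visit 4 bias, net of Monte Carlo error (mm Hg):**

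| Visit 2/3 correlations | OR 1 | OR 1.5 | OR 2 |
|---|---|---|---|
| 0.4375/0.4375 (equal slopes) | 0 | 0 | 0 |
| 0.55/0.50 | 0 | 0.15 | 0.24 |
| 0.65/0.55 | 0 | 0.29 | 0.48 |

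The SE is about 0.42 throughout, so the non-zero cells run from about 0.35 to 1.1 SE. The bias is positive, meaning that the fall in SBP is understated, when dropouts start higher. The sign reverses if they start lower.

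To judge how strong these ORs are: with 25% lost, a shift of 3.14 means that dropouts start 3.14/0.25 = 12.6 mm Hg above those seen at Visit 4. At OR 1.5 the shift is 1.93 and the gap is 7.7 mm Hg.

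**Stronger assumptions.** Correlations 0.75/0.60 with OR 3 give about 1.06 mm Hg, or 2.5 SE.

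**With baseline by visit added.** The bias is about 0 in every scenario (within Monte Carlo error of about 0.05), and the SE is 0.41 to 0.44. This holds only if LS means are evaluated at the mean baseline of all patients. For OR 1.5 to 2, even with the interaction, evaluating at the mean of patients with any post-baseline visit leaves about 0.3 to 0.7 mm Hg. Evaluating at the mean over analysed records leaves about 0.7 to 1.2.

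**The primary estimate under the same dropout.** The observed-case bias is about 0.5625 × shift: 0.5625 × 1.93 = 1.1 mm Hg at OR 1.5 and 0.5625 × 3.14 = 1.8 mm Hg at OR 2.

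**The case against.** The case against giving this much weight is strong, and most of it stands.

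- **Both conditions are needed and neither is documented.** A reader might infer that the MMRM is biased as specified, or whenever dropout is related to baseline. It is not: with equal slopes the bias is zero at any strength of dropout. The documents give no Visit 2 or Visit 3 correlations, no visit-specific SDs, and no link between dropout and baseline BP. If the visit SDs happened to keep r × SD constant, the bias would vanish even with falling correlations.
- **One SE is not a ceiling.** A reader might take about one SE as the maximum. It is only where the moderate scenarios end; the computed range is 0 to about 2.5 SE.
- **The MMRM is not the only analysis that reaches patients without a Visit 4 BP.** SAP section 5 plans last observation carried forward, worst-case imputation and regression imputation once more than 1% of outcomes are missing, which 25% dropout would trigger. Protocol 13.2.4 says that early leavers' last BP will be gathered and kept in the efficacy analysis.
- **The analysis is supportive.** Under the same dropout the primary observed-case mean is several times more biased than the MMRM as written.
- **Scale.** The SAP supplied covers Kazakhstan only. If enrolment follows sites (about 10 of 90, an assumption), that is 1916 × 10/90 ≈ 213 patients. The SE is then about √9 = 3 times larger, and the bias is about a third as large relative to it.

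What survives is the specification itself. Because SAP 9.1 names a group-by-visit term and no baseline-by-visit term, a single slope is the natural reading. The mechanism is confirmed by hand and by simulation, and the remedy carries no material SE penalty.

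**Conclusion.** The point holds in a limited form. The MMRM as written can give a biased Visit 4 LS mean under MAR when baseline slopes differ between visits and dropout depends on baseline BP. Under the moderate assumptions above the bias is 0.15 to 0.48 mm Hg, roughly 0.2 to 0.5, against an SE of about 0.42. It could be zero, or larger under stronger assumptions.

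Even 0.48 mm Hg is under 3% of the expected change (0.48/17.311 = 2.8%) and about half the planned 1 mm Hg half-width. It would not alter a conclusion about whether BP fell. The algebra is certain; the size rests on inputs that the documents do not supply. Severity is minor, and the change is a free improvement. Because the primary estimate is more exposed to the same dropout, it is worth having a supportive model that handles this case correctly.

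**What to change.** In protocol 13.2.2 and SAP 9.1:

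1. Add baseline SBP (DBP) by visit as a fixed effect, so that each visit has its own baseline slope.
2. Prespecify an unstructured covariance for the three post-baseline visits (six parameters) in place of a structure to be chosen later.
3. State that LS means are evaluated at the mean baseline of all patients in the Full Analysis Set, including those with no post-baseline BP, and not at the mean over analysed records or analysed patients. Without this, adding the interaction does not remove the bias.

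The cost is two degrees of freedom per model (three slopes in place of one), an explicit baseline value in the LS-means statement, and no new data. The SE is essentially unchanged.

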Medical history is history of diseases indicated before signing of the Informed Consent Form.

Concurrent medical conditions are those significant ongoing conditions or diseases that are present at signing of informed consent.

Comorbidities (concomitant disease) are diseases which occur after start of Edarbi[®] treatment and are not related to the Edarbi[®] treatment. Comorbidities may include not limited to cardiovascular disorders (coronary artery disease, peripheral artery disease, cerebrovascular disease), diabetes, chronic pulmonary artery disease, chronic kidney disease. The condition (ie, diagnosis) should be described.

Risk factors are conditions which increase probability of cardiovascular disease in patients with HTN at the moment of signing ICF. Risk factors are described in accordance with Russian guidelines "Diagnostics and treatment of hypertension" (2010).

Time of medical event/disease	How it should be documented
Birth to day before ICF signed	Medical history
At the moment of ICF signing	Risk factors
At the moment of ICF signing	Concurrent medical conditions
After ICF signing and start of Edarbi® treatment	Adverse Events

Page 18/31

After coding, medical history, risk factors, concurrent medical conditions and adverse events will be summarized and reported in accordance with denoted conventions (see. "Summary of study data").

Treatments to be documented in the study

All medications recorded in accordance with study protocol, including:

- Prior HTN treatment
- HTN treatment received during follow-up
- Concomitant medication

- will be summarized using denoted descriptive statistics (see "Summary of study data"). Number of subjects with these treatments will be summarized.

Edarbi® treatments will be registered in the CRF The following information about Edarbi® treatment will be collected:

- start date of Edarbi®,
- end date of Edarbi® treatment or prolongation of Edarbi® treatment,
- single and total dose, dose regimen,
- reason(s) for discontinuation of Edarbi ® treatment (if applicable).

Edarbi® should be administered according to the official prescribing information (The Russian SmPC). The starting dosage will be 40 mg per day. In case of insufficient efficacy, the dosage could be increased up to 80 mg per day.

HTN treatment

In case of combination HTN-treatment all co-medications for HTN treatment should be registered in Case Report Form. For every type of co-medication following data should be documented:

- INN, trade name,

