10. SAFETY ANALYSES

Unless specifically stated otherwise, the Safety Set (patients who have taken at least one dose of Edarbi®) will be used for all safety summaries and analyses.

All safety data will be included in data listings.

For relevant safety variables, early Withdrawal Visits will be assigned to the closest scheduled visit for the particular assessment that is being summarized.

Adverse Events

Prior to analysis, adverse drug reactions will be coded using MedDRA.

Incidence and characteristic of adverse drug reactions will be described and presented in summary tables using absolute frequencies and percentages;

Evaluation of AEs will consist of the determination of total number of AEs, total number of patients with at least one AE and the number of AEs, the number of patients with AE leading to discontinuation of the study treatment. The incidence and severity of all AEs will be summarized by System Organ Class and Preferred Term within SOC. Treatment discontinuation due to AEs will be tabulated

AEs reported in the study as well as AEs reported directly to authorities and to Takeda International Drug Safety according to section 11.3 and not captured in the study database will be extracted from the overall safety database and the study database and listed or tabulated in the final report in the standard way of presenting such data in a Periodic Safety Update Report (PSUR). In addition AEs will be tabulated for Edarbi treatment doses (if any dosage groups, e.g. 40 mg and >40-80 mg will be determined).

Interim safety analysis will be based on the data of first 470 patients who either achieved final study visit or discontinued the study.

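### Dose is raised when blood pressure response is poor, so the planned dose-response trend test and by-dose LS means are biased against the higher dose

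*Protocol*

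**What the plan says.** On dosing, Protocol 10.6.1 reads: "The starting dosage will be 40 mg per day. In case of insufficient efficacy the dosage could be increased up to 80 mg per day". SAP 7 repeats the rule. No other trigger for an increase is given.

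On analysis, Protocol 13.2.2 adds an MMRM of SBP (DBP) change to the primary interval: "Visit will be treated as a categorical predictor and baseline SBP (DBP) will be included as a covariate". Within it, "The dose-response trend hypothesis test will be conducted using the appropriate contrast statement for a linear (ordinal dose) trend", and then "Least Squares Means, the associated standard errors and 95% confidence intervals will be displayed by each individual dose group".

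SAP 9.1 repeats this model without the trend sentence and makes the dose display conditional: "in case if exposition assessment will reveal distinct dose groups, then group factor and group * visit interaction will be added to the model". SAP 2.4 and 4 restrict this SAP's analysis to the Kazakhstan data. SAP 11 asks for all MMRM regression coefficients, confidence intervals and p-values. SAP 8 adds a tabulation by dose if a significant share of patients, for example over 5%, switch dose. SAP 10 tabulates adverse events by dose if dose groups can be determined.

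SAP 9.3.1 lists subgroups by dose at initiation (including a 20 mg group) and by initial dose maintained throughout. Neither document says whether the MMRM dose group means starting, current, final or maximum dose.

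**The concern.** Under the stated titration rule, a patient reaches the higher dose because pressure on the lower dose stayed too high. Dose during follow-up is then a consequence of earlier response, and a between-patient comparison at Visit 4 partly measures who responded poorly at Visits 2 and 3. Baseline SBP does not correct this, because the titration decision uses on-treatment pressure.

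A reader of the trend test or the by-dose LS means could conclude, with a small p-value, that the higher dose lowers SBP less when titration alone produced the pattern.

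The adverse-event tables have a related gap. No rule assigns an event to the dose in force at onset or accounts for time on each dose, so an event that began before an increase could be counted under the higher dose.

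**Working it through.** **The plan's own figures.** Neither document gives a figure for a dose contrast. The sample-size inputs in Protocol 13.4 are SD 17.79, correlation 0.4375, mean SBP change −17.311, half-width 1 mm Hg and conditional probability 0.9. The SD of the difference is 17.79 × √(2 × (1 − 0.4375)) = 18.869. The exact conditional method returns 1437 pairs (probability 0.9027; stated 0.903), and 1437 / 0.75 = 1916. Both stated figures are reproduced. They concern the whole-sample paired mean, so the 1 mm Hg half-width is no yardstick for a dose contrast.

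**Why baseline adjustment is not enough.** Let r = 0.4375 be the correlation of each on-treatment visit with baseline, and ρ the correlation between on-treatment visits (not given; assumed). Given baseline, the correlation between the titration visit and Visit 4 is (ρ − r²)/(1 − r²), with r² = 0.1914:

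- ρ = 0.4375: 0.2461 / 0.8086 = 0.30
- ρ = 0.60: 0.4086 / 0.8086 = 0.51
- ρ = 0.75: 0.5586 / 0.8086 = 0.69

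Any positive value carries titration-visit pressure into Visit 4, so patients selected for an increase have higher Visit 4 SBP at the same baseline.

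**Simulation A, using document figures where they exist.** There are 1437 completers, with SD, r and mean change as above. The threshold is 140 mm Hg, the SBP target in Protocol 4.2. Assumed inputs: baseline mean 155 or 160; ρ of 0.4375, 0.6 or 0.75; dose raised with probability 0.5 or 0.9 when SBP is at least 140 at Visit 2 or 3. Group is the dose in force at Visit 4. The estimate is the higher-minus-lower dose difference in Visit 4 change, adjusted for baseline; positive means the higher dose looks worse.

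| True extra effect (mm Hg) | Range of mean estimate | Runs significantly inverted |
|---|---|---|
| 0 | +5.5 to +18.6 | at least 98% |
| −2 | +3.3 to +16.6 | at least 98% |
| −4 | +1.5 to +14.5 | 45% to 100% |
| −6 | −0.6 to +12.5 | 0% to 100% |

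The mean estimate is positive in 47 of 48 scenarios, including 35 of the 36 with a real benefit.

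The MMRM with group and group-by-visit terms (baseline mean 155, probability 0.7) gives +7.5 to +16.2 when the truth is 0 and +3.4 to +12.3 when it is −4. With truth 0, the raw unadjusted difference is smaller, +0.1 to +8.2. Adjusting for baseline therefore does not remove the bias here and makes it larger.

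**Simulation B, all inputs assumed.** Baseline mean is 155, true-level SD 10, mean effect −14, between-patient response SD 8 and visit error SD 8; dose is raised 60% of the time when SBP is at least 140.

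- True 0, −3, −5, −8: about +10, +7, +5 and +2.
- True −5, titration 30% to 90%: +2.2 to +8.5.
- True −5, response SD 4 to 12: +1.3 to +10.2.
- Response SD 4, 30% titration, true −5: about −0.7, the right sign but too small.
- Response SD 4, 60% titration, true −8: −1.7, again too small.

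**Checking remedies.** With dose as a time-varying covariate in an unstructured MMRM, and titration driven only by recorded SBP, the estimate is −0.04 to +0.09 when the truth is 0 and −3.94 to −4.14 when it is −4. By contrast, a display of SBP at the visit before and the visit after an increase shows a fall of about 3.6 mm Hg in Simulation B with no dose effect at all, which is regression to the mean.

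**The case against.** The strongest reply has four parts.

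*The analysis is additional.* This is correct. The MMRM and trend test supplement the primary interval, and no visible objective concerns dose-response. Protocol 13.2.4 also concedes that efficacy cannot be fully evaluated without a control. That section does not mention titration on response, however, and a prespecified hypothesis test will be read as evidence.

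*The SAP has dropped the trend test.* It has, for the Kazakhstan data. By-dose LS means remain, with exposure-derived groups and p-values. The protocol test still stands for the full study.

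*Dose group might mean starting dose.* This cannot be excluded, because the term is undefined. But one starting dose leaves a trend test nothing to compare, and SAP 9.1 draws its groups from exposure. Titrated dose is the natural reading.

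*The simulation inputs are largely assumed.* They are. The direction of the bias follows from the titration rule, but its size and the final sign depend on the inputs.

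Some stronger inferences fail. Starting-dose groups are not unbiased: they avoid the titration problem, but the physician chooses the dose, so they are open to confounding by indication. A patient who stops early with an adverse event need not appear under the lower dose, since some stop after an increase and SAP 9.3.1 allows several starting doses. Whether the trend test is the only formal test of its kind cannot be judged, because exploratory sections are redacted.

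**Conclusion.** The concern holds as a should-fix point. If dose group means titrated, final or maintained dose, the by-dose contrast is biased against the higher dose and often has the wrong sign. The illustrative size is about +10 mm Hg with no true dose effect and about +5 with a true −5. Across the document-anchored scenarios with no true effect it is +5.5 to +18.6.

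This rests on increases following on-treatment SBP of at least 140 mm Hg, and on assumed values for baseline mean, visit-to-visit correlation, response spread and titration frequency.

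A reader might infer that an inverted dose-response is certain, or that the study's main result is compromised. The documents support neither. With weak titration and little variation in response the sign can be right, and the primary interval for SBP change does not use dose. For adverse events, the documents show a missing attribution rule and no demonstrated misattribution.

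**What to change.** 1. Delete the dose-response trend test from Protocol 13.2.2. Alternatively, replace the between-patient dose group with a time-varying dose term in the MMRM, and state the assumption that titration depends only on recorded blood pressure.
2. Define dose group in both documents. Do not use titrated, final or maintained dose as a between-patient MMRM factor for inference.
3. If by-dose LS means are kept, group by dose prescribed at baseline where more than one exists, and label them non-causal because of confounding by indication.
4. Show titrated-dose results descriptively, labelled as confounded by response. State that any before-and-after-increase display includes regression to the mean.
5. In SAP 10, tabulate adverse events by the dose in force at onset, with approximate time on each dose. Dose regimen by visit and event start dates are collected (Protocol 10.3, 10.4, 11.2.2). No dose-change date is listed, and patients may attend between recorded visits, so state the assumed change date.
6. Reconcile the single starting dose in Protocol 10.6.1 and SAP 7 with the several starting doses in SAP 9.3.1.

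The cost is wording in Protocol 13.2.2 and SAP 9.1 and 10, plus modest programming. No new data are needed if the assumed change date is accepted. The downside is that the formal dose-response test is given up or rests on a stated assumption.
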